### **7.5.7 Hematology**

Hematology will include platelets, hemoglobin, red blood cell count, white blood cell count, and absolute neutrophil count with differential to be measured at Baseline, on Day 1, 3, and 5; Weeks 1, 2, and 4; Months 2, 3, 4, 6, 8, 10, 12, 15, 18, 21, and 24.

### **7.5.8 Clinical chemistry**

Sodium, potassium, chloride, calcium, magnesium, inorganic phosphate, blood urea nitrogen, creatinine, glucose, uric acid, AST, ALT, alkaline phosphatase, total bilirubin, total cholesterol, HDL, LDL, triglycerides, CPK, lipase, and amylase will be assessed at hospital affiliated laboratory. The blood chemistry will be measured at Baseline, on Day 1, 3, and 5; Weeks 1, 2, and 4; Months 2, 3, 4, 6, 8, 10, 12, 15, 18, 21, and 24. LDL and HDL will be measured only at Baseline, Week 4, Months 6 and 12.

Random or fasting plasma glucose values as needed to rule out or confirm suspected new onset of diabetes.

If the CPK level is above the upper limit of normal, CK-MB fraction will be measured.

If the total bilirubin concentration is greater than 1.5 times the upper limit of normal, total bilirubin should be differentiated into the direct and indirect reacting bilirubin.

### **7.5.9 Urine measurements**

Measurements will be taken for glucose, protein and quantitative protein/creatinine ratio by a mid-stream urine sample at Baseline, Day 1, 3, and 5; Weeks 1, 2, and 4; Months 2, 3, 4, 6, 8, 10, 12, 15, 18, 21, and 24.

### **7.5.10 Pregnancy and assessments of fertility**

Any pregnancy that occurs during study participation should be reported to the relevant regulatory authorities and the drug manufacturer. The pregnancy should be followed up to determine outcome, including spontaneous or voluntary termination, details of birth, and the presence or absence of any birth defects or congenital abnormalities.

Any female patient that becomes pregnant after the start of study medication should be discontinued and the patient switched to standard treatment. All pre-menopausal women who are not surgically sterile will have a serum pregnancy test at screening, and a urine pregnancy test if suspect, and at the end of study visit. Pre-menopausal women will also undergo pregnancy tests at 6 months, 12 months and the 24 months. A positive urine pregnancy test requires immediate interruption of study medication until a pregnancy is confirmed. If confirmed, the patient must be discontinued from the trial.

### **7.5.11 Viral serology**

Viral serology will be assessed at screening and Months 3, 6, 12, 18, 24. All patients will be tested for hepatitis B surface antigen (HBsAg), Hepatitis C, CMV, BKV and HIV at baseline per standard of care. Earlier tests  $\leq$  12 months, are acceptable. Any patients with a positive HBsAg, positive hepatitis C serology, or HIV will be excluded. If results are not available prior to randomization, the patient may be included. If results are later found to be positive, the patient will subsequently be dropped from the study and administered the standard care at MGTI.

### **Premature discontinuation from study medication**

For those patients who prematurely discontinue study medication prior to Month 24, the Premature Discontinuation of Treatment CRF should be completed. The date of last dose and reason for discontinuation of study medication should be clearly documented and all subsequent post-study follow-up evaluation forms should be completed at the appropriate time points. Patients who prematurely discontinue study medication due to death, lost to follow up or patient withdrew consent will not have any post-study follow up evaluations.

### **Premature study discontinuation and follow-up**

For all patients prematurely discontinuing study medication, a post-study follow-up contact will be made at 6, 12, and 24 months after transplantation, except in patients who prematurely discontinue study medication due to death, lost to follow up or patient withdrew consent. Information on allograft and patient survival, malignancies, rejection episodes, and current immunosuppressive regimen will be collected. A blood sample will also be collected for serum creatinine. All patients will be contacted 30 days after the last dose of study medication regarding Serious Adverse Event information. Graft loss, death and malignancy are Serious Adverse Events and should be entered on a SAE form and

reported to the relevant authorities during the follow-up period (beyond 30 days after the last dose). Other Serious Adverse Events that are related to study medication as assessed by the investigator should also be entered on a SAE form and reported to the IRB and other relevant authorities during the follow-up period.

Clinically notable laboratory abnormalities present at the time of discontinuation will be followed until the abnormality is no longer considered clinically significant.

This will be captured on the Study Completion CRF. Reason must be provided.

### **7.5.12 Appropriateness of safety measurements**

The safety assessments selected are standard for this indication/patient population.

## **7.6 Other assessments**

### **7.6.1 Resource utilization**

For resource utilization, all relevant information about initial hospitalization for initial transplantation and all follow-up hospitalizations post transplantation (in the transplant study center or all other centers, if any) will be recorded. The hospitalization data will include the main reason for admission, duration of hospitalization and number of days by level of care. All attempts should be made to collect RU variables in all patients throughout the duration of the study in order to avoid selection bias. There may also be circumstances when the collection of such data after completion of the study may be warranted. These data will be collected in the Hospitalization CRF and will be presented in a separate report.

### **7.6.2 Health-related Quality of Life**

The SF-36 is a widely used instrument to measure generic health status. It is a 36-item questionnaire that yields an 8-scale health profile as well as summary measures of individual patients. It has proven useful in monitoring generic and specific populations, comparing the relative burden of different diseases, differentiating the health benefits produced by different treatments, and in screening individual patients. The purpose collecting SF-36 data in this study is to compare the final health status of those on the ERL and low dose TAC arm of the trial to those on the ERL and low dose TAC which converts to MMF/MPA arm and to those on the MMF/MPA and standard dose TAC arm of the trial.

The eight profiles (scales) are: bodily pain, general health, vitality, mental health, physical functioning, role-physical, role-emotional and social functioning. The two summary measures are physical health and mental health.

Patients must complete the questionnaire before other clinical assessments at any given visit. The SF-36 can be administered in 5 to 10 minutes with a high degree of acceptability and quality. An appropriate person should be designated to facilitate self-administration. The administrator should not influence but can answer questions and address concerns and ensure that the questionnaire is filled out correctly and completely.

Completed questionnaires will be reviewed and examined by the investigator before the clinical examination for responses which may indicate potential AEs or SAEs. The

investigator should review not only the responses to the questions in the questionnaires but also for any unsolicited comments written by the patient.

If the occurrence of AEs or SAEs is confirmed, the physician must record the events as per instructions given in Section 7.5.1 of the protocol. Investigators should not encourage the patients to change the responses reported.

## **8 Safety monitoring**

### **8.1 Adverse events**

An adverse event is the appearance or worsening of any undesirable sign, symptom, or medical condition occurring after starting the study drug even if the event is not considered to be related to study drug. Study drug includes the investigational drug under evaluation and the comparator drug or placebo that is given during any phase of the study. Medical conditions/diseases present before starting study drug are only considered adverse events if they worsen after starting study drug. Abnormal laboratory values or test results constitute adverse events only if they induce clinical signs or symptoms, are considered clinically significant, or require therapy.

The occurrence of adverse events should be sought by non-directive questioning of the patient at each visit during the study. Adverse events also may be detected when they are volunteered by the patient during or between visits or through physical examination, laboratory test, or other assessments. All adverse events must be recorded on the Adverse Events CRF with the following information:

1. the severity grade (mild, moderate, severe)
2. its relationship to the study drug(s) (suspected/not suspected)
3. its duration (start and end dates or if continuing at final exam)
4. whether it constitutes a serious adverse event (SAE)

An SAE is defined as an event which:

- is fatal or life-threatening
- results in persistent or significant disability/incapacity
- constitutes a congenital anomaly/birth defect
- requires inpatient hospitalization or prolongation of existing hospitalization, unless hospitalization is for:
  - routine treatment or monitoring of the studied indication, not associated with any deterioration in condition
  - elective or pre-planned treatment for a pre-existing condition that is unrelated to the indication under study and has not worsened since the start of study drug
  - treatment on an emergency outpatient basis for an event not fulfilling any of the definitions of a SAE given above and not resulting in hospital admission

- social reasons and respite care in the absence of any deterioration in the patient's general condition
- is medically significant, i.e. defined as an event that jeopardizes the patient or may require medical or surgical intervention to prevent one of the outcomes listed above.

### **Protocol exempted events: Unusually severe rejection episodes**

Acute rejections are considered protocol exempted events. They should not be reported simply because they result in hospitalization thus meeting the criteria for SAEs. Acute rejection episodes will therefore not be routinely expedited to health authorities. However, acute rejections should be reported as SAEs if they are unusual in appearance, clinical course and/or are graft threatening.

Graft loss, death and malignancy are serious adverse events and should be entered on a SAE form for 30 days after last dose of study medication, including patients that prematurely discontinue from the study.

**Unlike routine safety assessments, SAEs are monitored continuously and have special reporting requirements; see Section 8.2.**

All adverse events should be treated appropriately. Treatment may include one or more of the following: no action taken (i.e. further observation only); study drug dosage adjusted/temporarily interrupted; study drug permanently discontinued due to this adverse event; concomitant medication given; non-drug therapy given; patient hospitalized/patient's hospitalization prolonged. The action taken to treat the adverse event should be recorded on the adverse event CRF.

Once an adverse event is detected, it should be followed until its resolution or until it is judged to be permanent, and assessment should be made at each visit (or more frequently, if necessary) of any changes in severity, the suspected relationship to the study drug, the interventions required to treat it, and the outcome.

Information about common side effects already known about the investigational drug can be found in the package inserts. This information will be included in the patient informed consent and should be discussed with the patient during the study as needed.

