**Recruitment/Treatment Periods:**

The recruitment period is planned for 24 months. The treatment period is 24 months. A biopsy will be required at Month 3, 12 and 24. Month 3 and 12 biopsies are done according to the institutional practice. No follow-up period is planned. Discontinued patients will be followed for renal function and incidence of efficacy failure at 3, 6, 12, and 24 months post-randomization. Serious adverse events will be recorded for 4 weeks after completing treatment.

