### **6.5.8 Study drug discontinuation and premature patient withdrawal**

Study drug must be discontinued and the patient withdrawn from the trial if the investigator determines that continuing it would result in a significant safety risk for that patient. The following circumstances require study drug discontinuation:

- Withdrawal of informed consent
- Pregnancy
- Use of immunosuppressive drugs other than those specified by protocol except those needed to treat acute rejection.
- If the everolimus trough level is  $\leq 3\text{ng/mL}$  and cannot be maintained.
- If tacrolimus is held for more than 14 days.
- Any other protocol deviation that results in a significant risk to the patient's safety

If study drug (ERL or MMF/MPA) is interrupted for longer than 21 consecutive days or more than 2 episodes of 7 days or longer, discontinuation of study drug should be considered and discussed with the sponsor.

For patients prematurely discontinuing ERL, a post-study follow-up contact will be made at Month 3, 6, 12, 18 and 24 after transplantation, except in patients who prematurely discontinue ERL due to death, lost to follow up or patient withdrew consent. Information will be collected on serum creatinine levels, urea, rejection episodes, graft loss/ re-transplant, malignancies, opportunistic infections, patient survival and current immunosuppressive therapy.

Patients who prematurely discontinued ERL will be followed for any serious adverse event (SAE) occurring within 30 days following the last dose of ERL. These SAEs should be reported to appropriate regulatory authorities.

In addition to these requirements for study drug discontinuation, the investigator should discontinue study drug for a given patient if, on balance, he thinks that continuation would be detrimental to the patient's well-being.

A Study Drug Discontinuation form should be completed, giving the date and primary reason for stopping the study drug.

Patients may voluntarily withdraw from the study for any reason at any time. They may be considered withdrawn if they state an intention to withdraw, or fail to return for visits, or become lost to follow up for any other reason. If premature withdrawal occurs for any reason, the investigator must determine the primary reason for a patient's premature withdrawal from the study and record this information on the Study Completion CRF.

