Patients who discontinue study drug prior to the 24 month treatment period will be contacted at scheduled months 6, 12, 18 and 24 visits to obtain follow-up information and should not be considered withdrawn from the study. Information will be collected on vital signs, hospitalizations, rejection episodes, lab results (proteinuria and serum creatinine),

graft loss/re-transplant, SAEs, malignancies, opportunistic infections, patient survival, CMV infections and immunosuppressive therapy. In addition, major adverse cardiac events (MACE) will be reported during the follow-up period as a Serious Adverse Event (SAE). These include acute myocardial infarction, congestive heart failure, percutaneous coronary intervention (PCI), automatic implanted cardiac defibrillator (AICD), coronary artery bypass graft surgery (CABG), cerebral vascular accident, and peripheral vascular disease.

Biopsies will be obtained at 3, 12 and 24 months post-transplantation for all patients who agree to have this procedure done. Biopsies will be obtained at 3 months and 1-year post-transplantation biopsies are performed as a part of standard institutional protocol.

If patients refuse to return for these visits or are unable to do so, every effort should be made to contact them or a knowledgeable informant by telephone to determine the information on survival status, graft loss/re-transplant, rejection episodes, malignancies, opportunistic infections and immunosuppressive therapies. Since patients will be followed even after discontinuation of study medication, the Study Completion CRF page should only be completed at Month 24 or earlier if the patient can no longer be followed, e.g. death, lost to follow-up, withdrawal of consent.

No study drug will be provided for patients who discontinue study medication prior to study completion at 24 months.

See Section 7 for the required assessments of these patients after study drug discontinuation.

For patients who are lost to follow-up (i.e. those patients whose status is unclear because they fail to appear for study visits without stating an intention to withdraw), the investigator /the study team will show "due diligence" by documenting in the source documents steps taken to contact the patient, e.g. dates of telephone calls, registered letters, etc.

Patients who are prematurely withdrawn from the study will not be replaced by an equal number of newly enrolled patients.

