## 7 Visit schedule and assessments

Table 7-1 lists all of the assessments and indicates with an “x” the visits when they are performed.

Patients should be encouraged to attend all visits on the designated day. However visit windows will be allowed of  $\pm$  1 day for Days 5 and 7,  $\pm$  3 days for Days 14, 21, and 28 visits,  $\pm$  1 week for Months 2 – 12 visits, and  $\pm$  2 weeks for Months 15 – 24 visits.

Patients who discontinue study drug before completing the study, and those who prematurely withdraw from the study for any reason, should be scheduled for a visit as soon as possible, at which time all of the assessments listed for the final visit will be performed.

Patients who discontinue study drug should also return for the assessments indicated in Table 7-1, including a blood sample for serum creatinine. If they refuse to return for these assessments or are unable to do so, every effort should be made to contact them or a knowledgeable informant by telephone when they refuse to return, and at 6, 12, and 24 months to determine the information on survival status, graft loss/re-transplant, rejection episodes, malignancies, opportunistic infections and immunosuppressive therapies. Since patients will be followed even after discontinuation of study medication, the Study Completion CRF page should only be completed at Month 24 or earlier if the patient can no longer be followed, e.g. death, lost to follow-up, or withdrawal of consent.

All patients will be contacted 30 days after the last dose of study medication regarding Serious Adverse Event information. Graft loss, death and malignancy are considered to be SAEs and should be entered on a SAE form and reported to the relevant regulatory authorities during the follow-up period (beyond 30 days after the last dose). Other Serious Adverse Events that are related to study medication as assessed by the investigator should also be entered on a SAE form and reported to the relevant regulatory authorities during the follow-up period.

Patients who prematurely discontinue study medication due to death, lost to follow up or patient withdrew consent will not have any post-study follow up evaluations.

At a minimum, patients will be contacted for safety evaluations during the 30 days following the last dose of study drug or last completed visit (whichever is later), including final contact at the 30-day point. Documentation of attempts to contact the patient should be recorded in the patient record.

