## **8.2 Serious adverse event reporting**

To ensure patient safety, every SAE, regardless of suspected causality, occurring after the patient begins taking study drug and until 30 days after the patient has stopped study participation must be reported to relevant regulatory authorities and IRB within 24 hours of learning of its occurrence. Recurrent episodes, complications, or progression of the initial SAE must be reported as follow-up to the original episode, regardless of when the event occurs. This report must be submitted within 24 hours of the investigator receiving the follow-up information. An SAE that is considered completely unrelated to a previously reported one should be reported separately as a new event.

The investigator must assess the relationship to study drug, complete and submit the SAE report forms. The original copy of the SAE reports and submission confirmation must be kept with the case report form documentation at the study site.

Follow-up information is sent to the same person to whom the original SAE Report Form was sent, using a new SAE Report Form stating that this is a follow-up to the previously reported SAE and giving the date of the original report. The follow-up information should describe whether the event has resolved or continues, if and how it was treated, whether the blind was broken or not, and whether the patient continued or withdrew from study participation.

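### The protocol gives conflicting rules for collecting serious adverse events after study drug stops, and the between-arm comparison does not say which window counts

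*Combined protocol and SAP*

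**What the plan says.** Section 6.5.8 states that patients who stop study drug before Month 24 are not withdrawn and are contacted up to Month 24. For their SAEs the protocol then gives these instructions:

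- **Section 8.1 (protocol exempted events):** graft loss, death and malignancy "should be entered on a SAE form for 30 days after last dose of study medication". Patients who discontinue early are expressly included.
- **Section 7:** the same three events are to be "reported to the relevant regulatory authorities during the follow-up period (beyond 30 days after the last dose". Other SAEs in that period are called for only when the investigator judges them related to study medication. Section 7.5, under premature study discontinuation and follow-up, repeats both rules.
- **Section 8.2:** every SAE, whatever its suspected cause, from first dose "until 30 days after the patient has stopped study participation must be reported to relevant regulatory authorities".
- **Section 6.5.8, everolimus paragraphs:** "Patients who prematurely discontinued ERL will be followed for any serious adverse event (SAE) occurring within 30 days following the last dose of ERL". The contacts listed there run to Month 24, but SAEs are not among the items collected at them.
- **Section 6.5.8, later paragraph on any study drug:** the items collected at Months 6, 12, 18 and 24 include "graft loss/re-transplant, SAEs, malignancies, opportunistic infections, patient survival, CMV infections and immunosuppressive therapy", with no limit by time or causality.
- **Synopsis, recruitment and treatment periods:** "Serious adverse events will be recorded for 4 weeks after completing treatment".

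SAE incidence is a secondary objective (Section 3.2). Section 10.5.2 compares it between arms with a Cochran-Mantel-Haenszel test and gives no counting window.

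**The concern.** Two of these conflicts cannot be read away. On graft loss, death and malignancy, Section 8.1 stops where Sections 7 and 7.5 continue. On all other SAEs, Section 8.2 asks for everything while Sections 7 and 7.5 ask only for related events after 30 days. Staff who follow the instructions written for patients off drug would comply with Section 7 and breach Section 8.2.

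At stake is the SAE comparison. If collection follows last dose, patients who stop early are observed for less time than those who stay on drug. If stopping differs by arm, SAE observation then differs by arm too. The related-only rule adds a causality judgement by an investigator who knows the treatment (Section 6.4). With no window in Section 10.5.2, the analyst must choose one after the data exist, and the data may have been collected under different rules for different patients.

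**Working it through.** The plan has no figure of its own to reproduce here. The check sets the rules side by side for one patient and measures the gap.

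**Inputs.** Follow-up to Month 24 (Section 6.5.8). Windows as listed above. One month is taken as 30.4375 days.

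**Patient who stops drug at Month 6 and is followed to Month 24.** Remaining follow-up is 18 × 30.4375 ≈ 548 days. Adding 30 days gives about 578.

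| Section | Events covered | Off-drug window |
|---|---|---|
| 8.1 | graft loss, death, malignancy | 30 days |
| 7 and 7.5 | graft loss, death, malignancy | to Month 24, about 548 days |
| 7 and 7.5 | other SAEs judged related | to Month 24, about 548 days |
| 7 and 7.5 | other SAEs judged unrelated | 30 days |
| 6.5.8, everolimus paragraph | any SAE | 30 days |
| 6.5.8, any study drug | any SAE | to Month 24, about 548 days |
| 8.2 | any SAE | about 578 days |

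The longest window is 578/30 ≈ 19 times the shortest. For a stop at Month 3 the longest is 21 × 30.4375 + 30 ≈ 669 days (22 times). For a stop at Month 12 it is 12 × 30.4375 + 30 ≈ 395 days (13 times).

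**What this could mean for capture.** The documents give no SAE rate, so a constant rate r is assumed and a range shown. The chance that at least one off-drug SAE falls inside a window of d days is 1 − exp(−r × d/365.25). For a Month 6 stop:

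| Assumed rate per patient-year | 30 days | 578 days |
|---|---|---|
| 0.25 | 2.0% | 33% |
| 0.5 | 4.0% | 55% |
| 1.0 | 7.9% | 79% |

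These are chances per patient who stops, not effects on the arm comparison. Section 10.5.2 compares incidences, so a patient who had an SAE before stopping is already counted under either window.

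**The end point of Section 8.2.** Its window runs from the end of study participation. The later part of Section 6.5.8 keeps patients off drug in the study. Section 6.5.5 says that a patient whose tacrolimus is held for more than 14 days is discontinued from the study. Section 6.5.7.2 says the same and then asks for follow-up to Month 24. For such a patient, Section 8.2 alone can be read as ending 30 days after that discontinuation or 30 days after Month 24.

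**The case against.** The strongest reply is that Section 8.2 already governs. Section 8.1 sends the reader there for SAE reporting, and the rule in 8.2 is arm-neutral and complete. The 30-day duty in Section 6.5.8 is a duty, not a cap, and Section 7 frames its 30-day safety contact as a minimum. Other text also picks up late events: Section 7.5.4 requires an SAE form for any infection leading to hospitalization, Section 6.5.8 treats major cardiac events as SAEs throughout follow-up, and Section 7.6.1 records all hospitalizations. This is a 48-patient pilot, and Section 10.5.2 treats exploratory tests as pointers only.

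Much of this stands. Most of the needed rule is already in the protocol, and many late events would leave a trace somewhere. It does not remove the conflict, because Sections 7 and 7.5 are the specific instructions for patients off drug and narrow what 8.2 requires.

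A reader might also infer more than the documents support:

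- **That everolimus is made to look safer.** Some stopping triggers are specific to everolimus, but no stopping rates by arm are given. The everolimus-only sentence in 6.5.8, read alone, adds a duty for those arms rather than removing one.
- **That a known share of patient-months is lost.** The 20% in Section 10.6 is a sample-size allowance for drop-out. It is not a count of patients who stop drug and remain followed, and true drop-outs give no later data under any window.
- **That a late admission for sepsis would go uncollected.** Sections 7.5.4 and 6.5.8 would both call for it.
- **That the synopsis adds a material conflict.** Four weeks and 30 days differ by two days, and the sentence can be read as concerning patients who complete treatment.

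**Conclusion.** The concern holds as an internal contradiction with a consequence for one analysis. Sections 8.1 and 8.2 each conflict with Sections 7 and 7.5, and Section 10.5.2 does not settle which window counts. Depending on the section followed, off-drug observation after a Month 6 stop is 30 days or about 578 days. That gap follows from the text and the calendar; the capture percentages rest on assumed SAE rates.

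Unequal observation by arm is a risk that depends on whether stopping differs by arm. Its direction and size cannot be derived from the documents. Graft loss and death still reach the primary composite through efficacy follow-up, so the harm is confined to SAE reporting and the SAE comparison. This should be corrected, but it does not undermine the primary analysis.

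**What to change.** 1. **State one rule in Section 8.2 for all three arms.** Collect every SAE regardless of causality, from first dose to the Month 24 contact or 30 days after last dose, whichever is later. Collection ends earlier only at death, withdrawal of consent or loss to follow-up.
2. **Align the other places to it:** the synopsis, Section 6.5.8 (refer to study drug rather than everolimus), Section 7, the follow-up text in Section 7.5, and Section 8.1.
3. **Reconcile Sections 6.5.5 and 6.5.7.2 with Section 6.5.8** on whether a patient taken off drug has left the study, so that the end of participation is unambiguous. This concerns follow-up status only; no view is taken on the rule for stopping treatment.
4. **State in Section 10.5.2** that the between-arm SAE comparison uses the 24-month window, with on-treatment plus 30 days as supportive.

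The cost is protocol wording and some additional SAE forms for unrelated late events. No new contacts are needed: the follow-up schedules in the synopsis, Sections 6.5.8, 7 and 7.5, and Table 7-1 all include Months 6, 12 and 24.
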